^c Perform 15 minutes (± 5 minutes) after the IMP injection is complete.

^d Collection of urine samples from participants who are unable to provide urine samples is not mandatory provided that a reasonable attempt has been made to collect the samples.

^e Baseline sample, not a screening sample; results not needed prior to dosing.

^f All participants will have sample collected for SARS-CoV-2 RT-PCR on Day 1. Only Cohorts 2 and 3 (treatment arms) will have a sample collected for quantitative RT-PCR on Day 1 and Day 8. For RT-PCR, the central laboratory should be used. For participants in Cohort 1 that have COVID-19 qualifying symptoms (Table 13) at any time during the study, an unscheduled sample will be collected for SARS-CoV-2 RT-PCR to confirm the participant is SARS-CoV-2 positive (Section 8.1.1).

^g For participants who receive AZD7442 via an IV infusion, a serum sample should be taken at the end of the infusion (and from the opposite side to the one used for the infusion).

^h All participants will be monitored on site for general safety, including injection/infusion site reactions and other hypersensitivity reactions, for at least one hour after IMP administration (Section 8.3.1).

ⁱ All participants will be contacted weekly starting from the time of IMP administration. During weekly contacts the Investigator will enquire about AEs, SAEs, MAAEs, and AESIs as well as any COVID-19 symptoms from the past 7 days.

Where necessary, the visit windows in the SoA can be used to collect samples across a number of days. When sample collection occurs over ≥ 2 days for a given study visit, participants are required to visit the site at least once per study visit. If practical, additional sample collection can take place at home visits as long as the samples are obtained per protocol by qualified personnel.

ADA, anti-drug antibody; AE, adverse event; AESI, adverse event of special interest; COVID-19, Coronavirus disease-2019; ECG, electrocardiogram; FU, follow-up; IMP, investigational medicinal product; IV, intravenous; MAAE, medically attended adverse event; NA, not applicable; PK, pharmacokinetic; RT-PCR, reverse transcriptase polymerase chain reaction; SAE, serious adverse event; SARS-CoV-2, severe acute respiratory syndrome coronavirus 2; SoA, schedule of activities.

Table 3 Schedule of Activities: Treatment and Follow-up Period for Participants Other Than Neonates – Main Study

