The dose volumes, infusion rates, and infusion times for each weight range were determined by considering the maintenance fluid rate and maintenance volume requirements. It is not recommended to deviate from these values unless the participant has a particular medical requirement that deems it necessary to adjust.

- AZD7442 (AZD8895 and AZD1061) infusion is to be administered through an IV administration set with a 0.2 or 0.22 µm low protein binding filter; acceptable configurations include an IV set containing an in-line filter or the attachment of a separate filter to the distal end of the IV tubing.
- AZD7442 (AZD8895 and AZD1061) infusion can be administered through the same IV line as other medications when local practices for flushing the line with each administration are followed.
- Administration set volume should not exceed 2 mL in order to minimize the flush volume.

- The IV line and catheter will be flushed according to local practices to ensure the full dose is administered. It is recommended to flush at the same rate as the drug infusion rate (listed in [Table 10](#)).
- **Important:** The timing of the PK sample must be well coordinated such that the PK sample is immediately obtained after the full dose is delivered. Sampling should occur immediately after the IV line and catheter are flushed.

The approximate infusion time and target rates are listed in [Table 10](#); however, if there are interruptions, the total allowed time must not exceed 4 hours with the infusion syringe maintained at room temperature, otherwise a new dose must be prepared from new vials.

Table 10 Doses and AZD7442 Admixture Concentration Selection per Cohort and Participant Weight Range for IV Administration

Participant weight range (kg)	Dose of AZD7442 (mg)	Concentration of AZD7442 Admixture (mg/mL) ^a	Volume of AZD7442 Admixture for administration (mL)	Infusion rate (mL/minute; mL/hour)	Approximate infusion time (minutes) ^b
Prophylaxis (Cohort 1)/Treatment – Outpatient (Cohort 2)					
≥ 1.5 to < 5 kg	50	20	2.50	0.1 mL/min; 6.0 mL/hour	25
≥ 5 to < 15 kg	110	50	2.20	0.3 mL/min; 18 mL/hour	7
≥ 15 to < 40 kg	300	50	6.00	0.8 mL/min; 48 mL/hour	8
≥ 40 kg	440	50	8.80	1.0 mL/min; 60 mL/hour	9
Treatment – Inpatient (Cohort 3)					
≥ 1.5 to < 5 kg	60	20	3.00	0.1 mL/min; 6 mL/hour	30
≥ 5 to < 15 kg	150	50	3.00	0.3 mL/min; 18 mL/hour	10
≥ 15 to < 40 kg	400	50	8.00	0.8 mL/min; 48 mL/hour	10
≥ 40 kg	600	50	12.00	1.0 mL/min; 60 mL/hour	12

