^a Refer to [Table 9](#) for instructions on preparation of the AZD7442 admixture.

^b Infusion time does not account for flush time

AZD7442 is to be administered as a single IV infusion (AZD8895 and AZD1061 co-administered).

IV, intravenous; min, minute.

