8.5.2 Pharmacokinetics

- Serum samples will be collected for measurement of serum concentrations of AZD7442 (AZD8895 and AZD1061) at either Day 4, 8, 11, or 15 (one sample) and Days 31, 92, 183, and 366 (one sample on each day), as specified in the SoA (Section 1.3). For participants who receive AZD7442 via an IV infusion, a serum sample should also be taken at the end of the infusion on Day 1 from the opposite side of the body. Serum samples should still be taken even if the participant is outside the visit window specified in the SoA.
- Samples may be collected at additional time points during the study if warranted and agreed upon between the Investigator and the Sponsor, eg, for safety reasons. The timing of sampling may be altered during the course of the study based on newly available data (eg, to obtain data closer to the time of peak or trough matrix concentrations) to ensure appropriate monitoring.
- Serum samples will be used to assess the PK of AZD7442 following IM and IV administration. Samples collected for analyses of AZD7442 serum concentration may also be used to evaluate safety or efficacy aspects related to concerns arising during or after the study.
- Samples will be collected, labeled, stored, and shipped, as detailed in the Laboratory Manual.
- AZD7442 PK parameters (eg, maximum serum concentration, AUC), if data permit, will be calculated based on AZD7442 serum concentrations following IM and IV administration.

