D8850C00006 Open-label, Uncontrolled, Single dose Study to Evaluate the Pharmacokinetics, Pharmacodynamics, and Safety of AZD7442 in Pediatric Participants Aged $\geq$ 29 Weeks Gestational Age to < 18 Years	IM and IV; dose is dependent on cohort indication and participant's weight. PK samples collected at end of infusion (IV only), on either 3, 7, 10 or 14 days post-dose, and then 28, 91, 182, and 365 days post-dose	~100 a	Phase I, pre-exposure prophylaxis, Treatment of COVID-19 in non-hospitalized participants, Treatment of COVID-19 in hospitalized participants

a The enrolment for this study was stopped early due to FDA feedback, therefore the full analysis set will only contain 46 participants.

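### The only Day 1 PK sample in IV participants has two specified times, end of infusion and end of line flush, and the SAP does not say how to handle a sample drawn between them

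*Protocol*

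**What the plan says.** Five places put the Day 1 IV sample at the end of the infusion and do not mention a flush.

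- Protocol Section 1.3, Table 2 footnote g, with the same text in Table 3 footnote h: "a serum sample should be taken at the end of the infusion".
- Protocol Section 4.2.1, which describes the extra IV sample in the same terms.
- Protocol Section 8.5.2: "a serum sample should also be taken at the end of the infusion on Day 1 from the opposite side of the body".
- SAP Table 5, in the row for this study: "PK samples collected at end of infusion (IV only").

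Protocol Section 6.2.2.2, in a bullet marked as important, gives a different time. It requires that "the PK sample is immediately obtained after the full dose is delivered", and then says "Sampling should occur immediately after the IV line and catheter are flushed". The same section explains that the flush is there so that the full dose is given, recommends flushing at the infusion rate, and limits the tubing: "Administration set volume should not exceed 2 mL in order to minimize the flush volume". Table 10 footnote b adds: "Infusion time does not account for flush time".

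The PK row of the schedule sends the reader to Section 8.5.2, not to Section 6.2.2.2.

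**The concern.** Table 10 footnote b separates infusion from flush, so the two instructions describe two different moments. The permitted set volume is large against dose volumes of 2.20 to 8.80 mL in Cohorts 1 and 2. When the syringe or bag empties, part of the dose can still be in the tubing.

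This is the only scheduled IV sample before Day 4. Cmax and tmax are primary PK parameters, and SAP Section 4.2.1 summarizes them by cohort, route and weight category. If sites applied the two instructions differently, Day 1 concentrations would not be comparable between sites, and the error would depend on weight band and so would not average out across the table. CL is computed as dose over AUC0-inf, so a low first point also passes into CL.

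**Working it through.** **Inputs.** Dose, admixture concentration, volume and rate come from protocol Table 10. The 2 mL limit comes from Section 6.2.2.2. The documents give no actual set volume, so 2, 1 and 0.5 mL are shown. The assumption is that the line holds undiluted admixture belonging to the measured dose.

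**Reproducing Table 10.** Volume = dose / concentration: 50/20 = 2.50 mL, 110/50 = 2.20 mL, 300/50 = 6.00 mL, 440/50 = 8.80 mL. Time = volume / rate: 2.50/0.1 = 25.0, 2.20/0.3 = 7.3, 6.00/0.8 = 7.5 and 8.80/1.0 = 8.8 minutes, against 25, 7, 8 and 9 in the table. All agree after rounding.

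**Largest undelivered share when the infusion ends** = set volume / dose volume. **Flush time** = 2 mL / rate.

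| Weight band, Cohorts 1/2 | Dose volume (mL) | 2 mL set | 1 mL set | 0.5 mL set | Time to flush 2 mL (min) |
|---|---|---|---|---|---|
| 1.5 to <5 kg | 2.50 | 80.0% | 40.0% | 20.0% | 20 |
| 5 to <15 kg | 2.20 | 90.9% | 45.5% | 22.7% | 6.7 |
| 15 to <40 kg | 6.00 | 33.3% | 16.7% | 8.3% | 2.5 |
| ≥40 kg | 8.80 | 22.7% | 11.4% | 5.7% | 2 |

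For Cohort 3 at 2 mL the shares would be 66.7%, 66.7%, 25.0% and 16.7%, but SAP Section 2 says that cohort has no participants.

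**From undelivered dose to AUC.** Protocol Section 4.2.1 equates 366 days with about 4 half-lives, so t1/2 is about 366/4 = 91.5 days and k = ln 2/91.5 = 0.00758 per day. Assume one compartment, let C0 be the concentration with the full dose in, and take the worst case of 90.9% undelivered, so that the Day 1 value is 0.091 C0. The next sample falls 3 to 14 days after dosing (Day 4 to Day 15). The curve rises over that interval, so the SAP's linear-up rule applies.

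- True area to time t: C0(1 − e^(−kt))/k. This is 2.97 C0 at 3 days and 13.28 C0 at 14 days.
- Computed area: t(0.091 + e^(−kt))C0/2. This is 1.60 C0 at 3 days and 6.93 C0 at 14 days.
- Total AUC0-inf: C0/k = 132.0 C0.
- Loss: (2.97 − 1.60)/132.0 = 1.0% at 3 days; (13.28 − 6.93)/132.0 = 4.8% at 14 days.

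CL rises correspondingly by 1/(1 − 0.010) − 1 = 1.0% to 1/(1 − 0.048) − 1 = 5.0%.

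**Cmax and tmax.** SAP Table 3 defines Cmax as the highest observed value. If the Day 1 value is too low, the Day 4–15 value replaces it. In the same one-compartment model that value is e^(−kt) = 0.978 C0 at 3 days and 0.899 C0 at 14 days, so Cmax would fall by about 2% to 10%, and tmax would move from minutes to days. A distribution phase would make the fall in Cmax larger and would raise the AUC effect somewhat. The documents give no distribution parameters, so neither is computed.

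**The case against.** The strongest reply is that the protocol already settles the timing. The schedule cell itself describes the IV sample as post dose, Table 16 footnote c uses the same term, and Section 6.2.2.2 is explicit. On that view the footnote is shorthand and a careful site would wait for the flush. Collection details are also left to a Laboratory Manual that is not available here. This softens the conflict and means early sampling cannot be presumed. It does not remove the conflict: Table 10 separates infusion from flush, and the schedule points to Section 8.5.2, which repeats the end-of-infusion time.

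A second reply is that safeguards exist. SAP Section 4.2.1.1 lists actual sample times and deviations from scheduled time. Section 4.1.3.1 makes relevant time-window deviations important, and such deviations may exclude data from the PK analysis set. These may still miss the problem. No end-of-flush time is named in either document, protocol Section 6.4 asks only for the date, and time if applicable, of dosing, and a site following the schedule has not clearly deviated.

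A third reply, on size, largely stands. A reader might take 23% to 91% as the bias in Cmax. The documents do not support that: 2 mL is the maximum set volume, actual sets are unknown, priming is not described, and the later sample puts a floor under Cmax. A reader might also infer that the problem is worst in the smallest children. The largest share is in the 5 to <15 kg band (91%), above the 1.5 to <5 kg band (80%), and IV numbers by weight band are not given. Nor does this one sample determine the population model, which starts from adult data including dense Phase I IV sampling and uses fixed allometric exponents.

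**Conclusion.** The contradiction is real and affects the only early IV sample. At the 2 mL limit it leaves at most 80%, 91%, 33% and 23% of a Cohort 1/2 dose undelivered (lightest to heaviest band), and proportionally less with a smaller set. That is an upper bound on dose left in the line, resting on the assumption that the line holds undiluted admixture from the measured dose.

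The plausible harm is a low observed IV Cmax and a tmax displaced to Day 4–15 where a site sampled before the flush, chiefly in the two lightest bands. The effect on AUC0-inf and CL is probably small, about 1% to 5% in the worst band under one compartment and a half-life near 91 days. The documents do not show that any sample was drawn early. The case for acting is that a primary PK parameter is exposed, the existing rules may not detect it, and the remedy is cheap.

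**What to change.** - **Protocol and SAP wording.** Make Table 2 footnote g, Table 3 footnote h, Sections 4.2.1 and 8.5.2 and SAP Table 5 refer to the Section 6.2.2.2 sampling time.
- **SAP, end of input.** Define the end of IV input as the end of flush wherever source records it.
- **SAP, known early samples.** Flag Day 1 samples known to have been drawn before the end of flush, and exclude them from the main IV Cmax, tmax and non-compartmental AUC summaries.
- **SAP, unconfirmed timing.** Keep the value, and report Cmax with and without these values as a sensitivity summary. Excluding all of them is not advised, because it could remove most of the IV Day 1 data.

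Enrolment has stopped, with 46 participants in the full analysis set (SAP Section 2), and each receives a single dose. The useful action is therefore mainly in the analysis. The cost is a check of source records for flush and sample times, and one extra summary.
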